#### **Four. V ARIABLES IN EVALUATION**

Data to collect:

\* PRIMARY VARIABLE:

*to. Variables related to ultrasound:*

To collect these variables, the GE VENUE will be used, the linear probe will be used (5.5–7.5 MHz) (General Electrics Healthcare, Madrid, Spain).

All patients will undergo a muscle ultrasound upon admission to the center and prior to upon discharge, using the usual muscle sweep technique. The ultrasound will be performed on the rectus femoris, vastus medialis, vastus lateralis and medial calf muscles. They will be measured:

- Muscle thickness in its cross section (in mm), in the plane of maximum thickness

in longitudinal sweep

- Cross-sectional area (in  $\text{cm}^2$ ) in the plane of maximum area in the scan longitudinal
- Angle of penetration (in degrees) of the medial twin, using the base of the angle the deep muscle fascia and as an angle the maximum inclination of the you muscle mass.

This exam will be carried out by 5 experienced physicians according to the criteria of the ACEP (American College of Emergency Physicians) and who carry out more than 10 studies ultrasounds per week and at least 3 years of experience in the performance and interpretation of ultrasound examinations. A reliability study will not be conducted given the limitation in the time and current healthcare pressure.

In addition, to avoid the possible bias that inter-operator variability would suppose in these circumstances, the research team was provided with a training program and designed internal training consisting of:

- Theoretical course on basic, systematic musculoskeletal ultrasound, medication, etc.
- Practical seminars in which an ultrasound machine and healthy models will be used to your measurement.
- Supervised practical training with real hospital patients until assessing an adequate measurement of at least 5 patients.
- The team of 5 doctors adequately trained in this technique were specific to this trial to avoid protocol deviations and any other form of interoperator variability.

\* SECONDARY VARIABLES:

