**2. Main objective:**

- Quantify the loss of muscle mass in hospitalized patients in areas of Medicine Inmate diagnosed with COVID-19.

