**Table 1. Study development**

*and. Statistic analysis*

The variables will be expressed by total numbers and percentages for the variables categorical, and central values with measures of dispersion (mean and standard deviation / median and interquartile range if not normal distribution) for quantitative variables.

For the comparisons, the following statistical tests will be carried out: Chi and obtaining of the odds ratio with 95% confidence intervals (for the comparison of variables qualitative); Student's t (and Spearman test) (to obtain the difference of means / ranges); and Pearson's R (to determine the correlation between the variables quantitative). The data will be analyzed using SPSS statistical analysis software.

20.0.

Data in absentia will not be charged and will be left as lost.

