**INTERNAL TWIN I ON ADMISSION**

Thickness      Sectional area      Angle of  
maximum (mm)    (cm2)                Penalty (in  
degrees)

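### The primary variable covers at least 9 ultrasound measures with no rule for choosing one, so the headline loss of muscle mass can be selected after the results are seen

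*Combined protocol and SAP*

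**What the plan says.** Section 4 (Variables in evaluation) uses a singular heading for the primary variable and then gives a list.

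- Muscles: "The ultrasound will be performed on the rectus femoris, vastus medialis, vastus lateralis and medial calf muscles".
- Measures: "Muscle thickness in its cross section (in mm), in the plane of maximum thickness"; cross-sectional area in cm², "in the plane of maximum area in the scan longitudinal"; and "Angle of penetration (in degrees) of the medial twin".
- Timing: "All patients will undergo a muscle ultrasound upon admission to the center and prior to upon discharge".

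The main objective (Summary item 10 and section 2.g) is a single quantity: "Quantify the loss of muscle mass in hospitalized patients in areas of Medicine Inmate diagnosed with COVID-19". The main hypothesis in the same places is directional, a progressive loss. The same thicknesses, areas and angle appear again among the secondary objectives. Muscle mass estimated by bioimpedance is listed as a secondary variable.

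The statistical analysis paragraph in section 5 offers generic tests, such as "Student's t (and Spearman test) (to obtain the difference of means / ranges". It gives no primary analysis, hierarchy or multiplicity rule.

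There are two sample-size statements. Summary item 11 uses a one-sided contrast with alpha 0.05, beta 0.2 and a 20% loss, giving 64 subjects. Section 3 uses a 95% confidence interval, 3% precision and an expected loss of about 3%, giving 124 patients. Neither says which muscle or measure its percentage refers to.

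The data collection notebook (Annex I) has blocks for two legs, marked D and I, for example "INTERNAL TWIN I ON ADMISSION".

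**The concern.** The main result is meant to be one number for the loss of muscle mass. The plan supplies many candidates for that number, in three units (mm, cm² and degrees), and no rule connecting any of them to it. It does not say whether change is absolute or percent, or how two legs would be combined.

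The main risk is to the estimate. If the headline figure is chosen because it shows the clearest loss, it is biased upward, and its ordinary 95% interval no longer has its stated coverage. This needs no hypothesis test to occur. The second risk is a false claim of loss. The hypothesis is directional, the Summary mentions a one-sided contrast and t tests are planned, so a statement that muscle was lost could rest on whichever measure crosses the threshold.

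**Working it through.** **1. The plan's own sample sizes.** Section 3: N = z²·p(1−p)/d² with z = 1.96, p = 0.03, d = 0.03, so 1.96² × 0.03 × 0.97 / 0.03² = 124.2. This reproduces 124. The Summary's 64 is reproduced as the number per group for comparing proportions of 20% and 40%, one-sided 5%, 80% power. Both are formulas for proportions. Neither uses an SD of change in any ultrasound measure, so neither identifies a primary measure indirectly.

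**2. Number of candidates.** From section 4: 4 muscles × 2 measures + 1 angle = 9. If every measure is taken on both legs at both visits: 2 × 9 = 18. The second figure is an inference from Annex I. As the text was extracted, Annex I shows both legs at both visits only for calf thickness and area. The thigh muscles appear as D at entry and I at discharge, and the calf discharge blocks repeat a thickness label where the angle would be expected. These may be faults of extraction or of the form layout, so they are not counted as errors. They do mean that 18 cannot be treated as established, and the working range is 9 to 18.

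**3. Bias from reporting the largest.** Assumptions: k estimates of change, each divided by its standard error, jointly normal with common correlation r, and equal true changes on that standardised scale. The documents give no correlations, so r is varied. The expected excess of the largest estimate over the truth is E[max of k standard normals], by simulation with at least 200,000 draws.

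| r | k = 9 | k = 18 |
|---|---|---|
| 0 | 1.5 SE | 1.8 SE |
| 0.3 | 1.2 SE | 1.5 SE |
| 0.5 | 1.0 SE | 1.3 SE |
| 0.8 | 0.7 SE | 0.8 SE |

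**4. Chance of at least one nominal loss when there is none.** For r = 0 this is exact: 1 − (1 − a)^k, where a is the error rate per measure in the direction of loss. A one-sided 5% test has a = 0.05. A two-sided 95% interval lying wholly on the loss side has a = 0.025.

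- k = 18, a = 0.05: 1 − 0.95^18 = 0.603.
- k = 9, a = 0.025: 1 − 0.975^9 = 0.204.

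With correlation, by the same simulation:

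| r | k = 18, one-sided 5% | k = 18, two-sided 95% CI | k = 9, one-sided 5% | k = 9, two-sided 95% CI |
|---|---|---|---|---|
| 0 | 60% | 37% | 37% | 20% |
| 0.3 | 42% | 26% | 29% | 17% |
| 0.5 | 33% | 20% | 23% | 14% |
| 0.8 | 19% | 11% | 15% | 8% |

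**5. Cost of keeping all measures co-equal.** Bonferroni intervals of the same half-width multiply N by (z for 0.05/k ÷ z for 0.05)², two-sided. For k = 9: (2.773/1.960)² = 2.00, so 124.2 becomes about 249. For k = 18: (2.991/1.960)² = 2.33, so about 289. One pre-specified primary needs no such inflation.

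**The case against.** The strongest reply is that this is an observational study whose aim is to quantify. Its body text plans a 95% interval, and the secondary objectives commit to analysing every named muscle. On that reading family-wise error is a side issue, and the other results will be visible beside the headline. Much of this stands. The one-sided 5% occurs only in the Summary's sample-size sentence, and the planned analysis of all muscles limits outright concealment. It does not settle which result answers the main objective, and selection biases an estimate whether or not a test is made.

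A reader might go further and infer that the plan runs 18 primary tests at 5% each, with a 60% chance of a false finding. The documents do not support that:

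- The count of 18 is not stated, and Annex I as extracted does not confirm it.
- The statistical paragraph sets no level per test and does not say that each measure will be tested.
- The 60% requires independence, which is implausible for thickness and area of the same muscle or for two legs of one patient.
- The null of no loss differs from the protocol's own expectation of a loss of about 3%.

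Nor can the bias be converted into percent of muscle lost. It is in standard errors, it assumes equal standardised changes, and the documents give no SD.

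**Conclusion.** The concern holds in a limited form. The plan leaves at least 9 measures, possibly 18, as one undifferentiated primary variable, and nothing in it prevents choosing the headline after the results are seen. This is more than missing detail, because the main objective is itself the magnitude that such a choice would distort.

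The size is illustrative: an overstatement of about 0.7 to 1.8 standard errors if the largest estimate is reported. For a false claim of loss, the range is about 8% to 20% on the milder reading (9 measures, two-sided 95% intervals) and about 19% to 60% on the harsher one (18 measures, one-sided 5%). These ranges rest on assumed correlations of 0 to 0.8. The defect itself depends neither on the exact count nor on the correlations. For an observational study it is a change that should be made, and it does not invalidate the design.

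**What to change.** Before any change data are examined, specify one primary measure: one muscle, one measurement, a leg rule that matches what the notebook records at both visits, and percent change from admission to discharge. Percent change in rectus femoris cross-sectional area would serve as an example; nothing in the documents favours it over the others. Report it with a two-sided 95% confidence interval. Fixing the choice only at data lock would be too late, since the plan describes no blinding and the changes could be seen as they accrue.

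Make all other ultrasound measures secondary. Report every one as an estimate with its interval, or apply Holm adjustment if they are tested. Confirm in Annex I which leg is measured at which visit, and that the angle is recorded at discharge.

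State which measure the sample-size figures refer to, and give an assumed SD of its change with the source of that assumption.

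Most of this is wording. The real costs are committing to one muscle and measure in advance, and finding or assuming an SD that the documents do not supply.

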### ***11. Study population and total number of patients***

Patients over 18 years of age who are admitted to the hospital and whose primary diagnosis and reason for staying is COVID-19 pneumonia. The prevalence of sarcopenia in hospitalized patients is 15-20%. Assuming a alpha risk of 0.05 and beta risk of 0.2 in a one-sided contrast, 64 subjects are required to detect a difference equal to or greater than 20% loss of muscle mass. It has been an estimated loss to follow-up rate of 0%.

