#### *c. Inclusion and exclusion criteria.*

Patients who meet the following criteria will be included:

- Over 18 years old, men or women.
- Main diagnosis is pneumonia due to COVID-19

- Subjects who, after having received the information on the design, the purposes of the project, the possible risks that may arise from it and that in any moment they can deny their collaboration, verbally grant their consent to participate in the study.

The exclusion criteria to participate in the study are:

- Refusal of the patient to participate in the study.
- Present a malignant neoplasm in active phase except Ca spino- or basal cell in local stage
- Clinical situation of agony.
- Amputation of limb (s).

*d. Origin of the data:*

The data will be collected prospectively.

*and. Schedule and expected date of completion:*

The study will begin in **February 2021**, with an estimated duration of **3 months** (1 month for application, 1 month for data collection, 1 month for results analysis and preparation of articles and / or communications).

*and. Sample size:*

Patients over 18 years of age who are admitted to the hospital and whose primary diagnosis and reason for staying is COVID-19 pneumonia. For a 95% confidence interval, with a precision level of 3%, an estimated loss in about 3% of muscle mass in COVID-19 patients for an admission less than 10 days, we hope to recruit 124 patients. A loss to follow-up rate has been estimated 0%.

Subjects will be followed up during hospitalization and one month after consultation. recruitment. The 30-day follow-up will be done by reviewing the history

clinic, and a telephone contact will be made.

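### The plan neither records who performs each scan nor keeps admission values from the discharge operator, although a shift of 1 to 2 points would matter against the expected 3% loss

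*Combined protocol and SAP*

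**What the plan says.** Section 4 (primary variable) has the rectus femoris, vastus medialis, vastus lateralis and medial calf scanned on arrival and before discharge. Thickness and area are read at the plane where each is largest, found during a longitudinal sweep. Five experienced physicians share the work. The section recognises that differences between operators could bias the results, and then states: "A reliability study will not be conducted given the limitation in the time and current healthcare pressure". The safeguards are experience thresholds, a course, seminars and supervised practice on at least 5 patients. No numerical agreement criterion is set. The section adds that the five trained doctors "were specific to this trial to avoid protocol deviations and any other form of interoperator variability".

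The sample size text in Section 3 sets the scale: "with a precision level of 3%, an estimated loss in about 3% of muscle mass", and "we hope to recruit 124 patients". Item 11 of the Summary uses another scale: "64 subjects are required to detect a difference equal to or greater than 20% loss of muscle mass".

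The plan does not say:
- who scans at which visit, or whether the same physician does both scans of a patient;
- whether the discharge operator may see the admission values;
- in the available Annex I text, who made each scan or when. The ultrasound blocks hold measurements only, whereas the Barthel fields in the same notebook carry a date;
- how operator differences enter the analysis. The statistical analysis part of Section 5 has no operator term.

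No SD, intraclass correlation or coefficient of variation for the measurements is given anywhere.

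**The concern.** The main objective is to quantify loss, and the main hypothesis is directional: patients lose muscle. The design compares each patient with his or her own earlier scan and has no control group, so a systematic difference between how admission and discharge scans are read goes straight into the estimate.

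There are two routes. First, an operator who expects loss and can see the admission value may, without intending to, settle on a plane that gives a smaller reading. Such a shift runs in the hypothesised direction and does not shrink with sample size. Second, if the operators who tend to read high do more of one visit's scans, the mean change absorbs their difference. This can go either way.

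If the operator is not recorded at the time of the scan, the second route cannot be examined in the analysis, and the information may not be recoverable later.

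**Working it through.** **The plan's own figure.** The inputs in Section 3 are a 95% interval (z = 1.96), an expected loss of 3% and a precision of 3%. The section states no formula, but the precision formula for a single proportion reproduces its number:

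n = z² p(1 − p)/d² = 1.96² × 0.03 × 0.97 / 0.03² = 124.2, against 124 stated.

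This calculation contains no SD of change and no measurement error. The planned interval around the expected loss is 3 ± 3, about 0 to 6%.

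All error sizes below are assumptions, in percentage points of the muscle measure, because the documents give none.

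**Expectation shift.** A consistent shift b at discharge moves the mean change by b at any n.
- b = 1 to 2 is 1/3 to 2/3 of the expected 3, and 1/20 to 2/20 (5 to 10%) of the Summary's 20.
- With half-width 3, SE = 3/1.96 = 1.53. Coverage of the 95% interval is Φ(1.96 − b/SE) − Φ(−1.96 − b/SE): 90% for b = 1 and 74% for b = 2.

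**Operator mix that differs between visits.** If 20% of scans move from higher-reading to lower-reading operators between visits, and the two sets read 5 to 10 points apart, the bias is 0.20 × 5 to 0.20 × 10 = 1 to 2 points.

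More generally, let s be the between-operator SD, and let a_k and d_k be operator k's shares of admission and discharge scans. The SD of the operator contribution to the mean change is s × √Σ(a_k − d_k)².

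| Allocation of the five operators | Multiplier of s | s = 3 | s = 5 |
|---|---|---|---|
| Independent random at both visits, n = 124 | √(2 × 0.8/124) = 0.114 | 0.34 | 0.57 |
| Shares 40/30/10/10/10 at admission, reversed at discharge | √0.26 = 0.51 | 1.5 | 2.5 |
| Two operators at admission, the other three at discharge | √(1/2 + 1/3) = 0.913 | 2.7 | 4.6 |

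In the last row the chance of a spurious mean shift of at least 3 points is 27% for s = 3 and 51% for s = 5. That row is an extreme that the plan does not describe. It shows only that the answer depends on an allocation the plan leaves open.

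**Random error.** Let e be the within-operator SD per scan. The measurement part of the SD of change is √(2e²) with the same operator and √(2s² + 2e²) with different operators. For e = 3 to 5 and s = 2 to 6:
- same operator: √18 to √50 = 4.2 to 7.1;
- different operators: √26 to √122 = 5.1 to 11.0.

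Treating errors as independent, the largest value gives a half-width of 1.96 × 11.0/√124 = 1.9 points from measurement alone, inside the planned 3.

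**The case against.** The strongest reply is that the sponsor disclosed the choice and mitigated it. Section 4 gives the reason for omitting a reliability study, sets experience thresholds, requires supervised practice and limits scanning to a dedicated team. The measurement plane follows a stated rule, and examinations are archived digitally, so stored images might be measured again. With five operators sharing both visits in similar proportions, the operator contribution to the mean has an SD of at most about 0.6 points for s up to 5. Random error does not threaten the planned precision either. Every bias size used here is assumed, and against the Summary's 20% a shift of 1 to 2 points is small.

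Most of this stands, and it limits the point. What it leaves open:
- A similar operator mix at both visits is neither required nor checkable without an operator code.
- Averaging does not remove an expectation shift.
- Operator noise stays in the individual changes used for the secondary objectives on correlations, treatment and length of stay.
- The image archive helps only in part: probe position, pressure and choice of plane are fixed when the image is taken.
- Training and experience may reduce these effects, but nothing planned measures by how much.

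Masking has its own limit: the operator still knows that a discharge scan is a discharge scan. Hiding the earlier values removes the target to read towards, not the expectation of loss.

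**Conclusion.** The point holds as a low-cost improvement to how the primary measurement is recorded and protected. With an expected loss of about 3%, no control group and no measurement-error data, the plan leaves two routes for systematic error open and provides no means to examine one of them. Under assumed shifts of 1 to 2 points, the bias would be one to two thirds of the expected loss. The two benchmarks in the documents (3% with 124 patients, 20% with 64) need reconciling, and the importance of this point depends on which applies.

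A reader might infer more than the documents support:
- *That these effects equal the 3% result.* The assumed biases of 1 to 2 points do not reach 3 singly. A larger shift needs an operator split between visits that no section describes.
- *That expectation bias will occur.* No section says the discharge operator holds or consults the admission values; the plan only fails to prevent it.
- *That measurement noise ruins the planned precision.* The largest assumed SD gives a half-width of about 1.9 points.
- *That operators are certainly not recorded.* Annex I was read from a garbled PDF extract, some pages were unavailable, and Section 6 mentions an electronic CRF whose fields are not shown. The statement covers the available text only.

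**What to change.** 1. Add an operator code and a scan date to each admission and discharge ultrasound block in Annex I and in the electronic CRF.
2. Record the discharge scan on a separate sheet, and state in Section 4 that the operator is not shown the admission values.
3. Add to the statistical analysis part of Section 5 a sensitivity analysis of the admission-to-discharge change, either with an operator effect or restricted to patients scanned by the same operator at both visits. This addresses operator differences only; item 2 is the protection against expectation.

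The cost is two fields per block, minor handling effort for the separate sheet, and one extra analysis. It needs no additional scan, reader or visit, so the time and workload reasons given for omitting a reliability study do not apply. I would not ask for the same operator to be scheduled at both visits: an operator who remembers the admission scan is no longer masked to it.

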***to. Demographic variables:***

- Age. Sex.

***b. Clinical variables:***

- Symptoms and time of evolution.

- Usual treatments.

- Previous illnesses.

- Barthel scale prior to admission and discharge.

***c. Variables related to physical examination:***

- Blood pressure (systolic, diastolic), heart rate (HR), respiratory rate (FR), oxygen saturation (SO2), Temperature (T°).

***d. Analytical and image variables:***

- Upon arrival: blood count (Hb and leukocytes - Neutrophils and Lymphocytes), biochemistry (creatinine, urea, CRP, AST, ALT, IL-6) and arterial blood gas (pO2, pCO2, lactate, pH). In the pertinent indications, it will be collected if available: Procalcitonin, CK, LDH, NT-ProBNP, D-Dimer, Troponin I.

- Control analysis: Hemoglobin, leukocytes, lymphocytes, Albumin, prealbumin, Total proteins, Calcemia, Phosphataemia, Ferritin, Vitamin D, Folic Acid, Vitamin B12, Creatinine, Cholesterol, Triglycerides.

- Chest X-ray and / or chest CT.

